Cholera remains a major public health problem in Asia, Africa, and Latin America. In regions where cholera is endemic, children are disproportionately affected in comparison to adults, and mortality remains high in the absence of adequate treatment. Antimicrobial therapy facilitates the treatment of cholera by reducing the duration and volume of diarrhea by approximately half. Options for antimicrobial treatment of childhood cholera is currently limited by the increasing prevalence of strains of *V. cholerae* resistant to the agents that have been used to treat this infection in children - furazolidone and trimethoprim-sulfamethoxazole - and the absence of a proven effective single dose therapy.

In this proposed study to be conducted at the International Centre for Diarrhoeal Disease Research, Bangladesh (ICDDR,B), we will compare clinical and bacteriologic efficacy of a single, 20 mg/kg dose (maximum of 1.0 gram) of oral suspension of a newer macrolide, azithromycin, and a 3-day course of the oral suspension of the older macrolide, erythromycin, administered in a dose of 12.5 mg/kg (maximum individual dose of 500 mg) every 6 hours in the treatment of children with clinically severe cholera due to *V. cholerae* O1 or O139 infection. The latter drug is the current treatment of choice for children with cholera at the ICDDR,B. Azithromycin has a longer half-life than erythromycin, attains very high stool concentrations, and has less adverse events than erythromycin. Treatment will be random, and will be blinded to investigators and patients.

Patients eligible for study will be male (1-15 years of age) or female (5-15 years of age), who have watery diarrhea of ≤ 24 hours and signs of severe dehydration (WHO guidelines), and who have cholera vibrios identified on dark-field microscopic screening of stools. Only those patients who have ≥ 20 ml/kg body weight of stool during a 4 hour observation period following initial rehydration period will be entered into the study; only patients from whom *V. cholerae* O1 or O139 is isolated, and who stay in-hospital for three or more days will be eligible for analysis. Written informed consent will be required from the parents/guardians of all children for their inclusion in the study. Patients will be asked to remain in hospital for full five days from the initiation of drug therapy, and to return for a follow-up visit ten days after discharge. Cultures of stool will be obtained on admission to the study, and daily during hospitalization. Stool will be collected, and the volume of watery stool measured for every six hour period of the study. Major outcomes to be compared in the two treatment groups will be clinical success of therapy, defined as resolution of diarrhoea within 96 hours of initiation of study drugs, and bacteriologic success of therapy, defined as the inability to isolate the infecting strain of *Vibrio cholerae* O1 or O139 after 48 hours of therapy. Other outcomes measures examined will be the incidence of adverse reactions to drugs in the two treatment groups, the duration of watery diarrhea and positive stool cultures, and the total volume of watery/liquid stools during study.

Azithromycin is active against multiply-resistant strains of *V. cholerae* O1 or O139, it is safe for use in children, and it is widely available. If single-dose of azithromycin is found to be effective in the treatment of cholera in this study, it will be a considerable advance in treatment of cholera in children; effective single-dose therapy of childhood cholera has not been previously identified with any drug.

Principal Investigator: Last, first, middle: [name]

KEY PERSONNEL (List names of all investigators including PI and their respective specialties)

Name	Professional Discipline/ Specialty	Role in the Project
1. [name]	Internal Medicine	Principal investigator
2. [name]	Internal Medicine	Co-investigator
3. [name]	Pediatrics and Infectious Diseases	Co-investigator
4. [name]	Biochemistry	Research Officer

DESCRIPTION OF THE RESEARCH PROJECT

Hypothesis to be tested:

Concisely list in order, in the space provided, the hypothesis to be tested and the Specific Aims of the proposed study. Provide the scientific basis of the hypothesis, critically examining the observations leading to the formulation of the hypothesis.

The hypothesis of this study is that in the treatment of cholera due to *V. cholerae* O1 or O139 in children aged 1-15 years, a single, 20 mg/kg dose (maximum of 1.0 gram) of azithromycin suspension will be as effective as the conventional, 3-day, multiple dose therapy with erythromycin suspension administered in a dose of 12.5 mg/kg (maximum individual dose of 500 mg) every 6 hours.

Specific Aims:

Describe the specific aims of the proposed study. State the specific parameters, biological functions/ rates/ processes that will be assessed by specific methods (TYPE WITHIN LIMITS).

The specific aims of the protocol are as follows:

1. Primary Aim

The primary aim of this study is to compare the clinical as well as bacteriologic efficacy of a single, 20 mg/kg dose (maximum of 1.0 gram) of azithromycin oral suspension with the conventional 3-day, 12.5 mg/kg (maximum individual dose of 500 mg) 6 hourly dose of erythromycin oral suspension in the treatment of clinically severe cholera in children due to *V. cholerae* O1 or O139.

2. Secondary Aims

The secondary aims of this study are:

- 2.1 To determine the serum and stool concentrations of both study drugs at specified times, and also to determine their serum half-lives.
- 2.2 To determine the minimum inhibitory concentration of *V. cholerae* O1 and O139 to the study drugs.
- 2.3 To monitor and compare the incidence, type and severity of adverse events in association with the study drugs.

Background of the Project including Preliminary Observations

Describe the relevant background of the proposed study. Discuss the previous related works on the subject by citing specific references. Describe logically how the present hypothesis is supported by the relevant background observations including any preliminary results that may be available. Critically analyze available knowledge in the field of the proposed study and discuss the questions and gaps in the knowledge that need to be fulfilled to achieve the proposed goals. Provide scientific validity of the hypothesis on the basis of background information. If there is no sufficient information on the subject, indicate the need to develop new knowledge. Also include the **significance and rationale** of the proposed work by specifically discussing how these accomplishments will bring benefit to human health in relation to biomedical, social, and environmental perspectives. (DO NOT EXCEED 5 PAGES, USE CONTINUATION SHEETS).

Cholera remains a major public health problem in Asia, Africa and Latin America. Its continued importance is reflected in the hundreds of thousands of cases, and tens of thousands of deaths that occurred when the seventh pandemic of cholera reached South America in 1991, the tens of thousands of deaths that have occurred among Rwandan refugees in the last two years, and the massive epidemics of cholera that occurred following the appearance of a new serogroup of cholera, *V. cholerae* O139, in Asia in 1993.

In countries where cholera is endemic, rather than epidemic, the majority of cholera morbidity and mortality occurs in children. Infection with *Vibrio cholerae* O1 or O139 is far more likely to cause dehydration than any of the other watery diarrheas of childhood, including those caused by enterotoxigenic *E. coli* and rotavirus [1]. If not effectively treated, cholera can lead to severe dehydration, hypovolemic shock, metabolic acidosis, and death within a few hours of the onset of disease. The explosive epidemic form of cholera is associated with much higher case-fatality rate, as was demonstrated during the 1994 cholera epidemic among Rwandan refugees in Goma, Zaire when an estimated 20,000 persons died from cholera in a 4-week period [2].

Fluid replacement and antimicrobial therapy are the mainstays of therapy of moderate to severe cholera. Antimicrobials reduce the volume and the duration of diarrhea by half. This in turn reduces the need for rehydration fluid and shortens the duration of hospitalization. Moreover, they shorten the duration of fecal excretion of *V. cholerae* and reduce transmission of infection to others [3-5]. All of these effects make antimicrobial therapy of cholera a cost-effective intervention.

Tetracycline, chloramphenicol, doxycycline, furazolidone, trimethoprim-sulfamethoxazole and erythromycin are all effective in the treatment of cholera when given for 3-5 days [3,6-8]. Single dose tetracycline and doxycycline therapy are also effective in the treatment of cholera, although bacterial eradication is slower than with multiple dose therapy. Ciprofloxacin is also effective in the treatment of cholera in multiple doses, and we have recently demonstrated that a single dose of ciprofloxacin is more effective than single dose doxycycline therapy of cholera in adults [9]. Tetracycline and doxycycline, however, are not recommended for use in children <8 years of age, and in pregnant and lactating women; chloramphenicol is a relatively toxic drug; and newer quinolones including ciprofloxacin are not recommended for routine use in children. Although of toxicity with any of these drugs is small when used for short courses of therapy, such as with cholera, there remains a reluctance to use these drugs in children, and they often are not available in a liquid formulation that would assist in administration to children.

Treatment of cholera in children has been further complicated by the emergence of multiply-resistant strains of *V. cholerae*. Strains resistant to tetracycline (which also implies resistance to doxycycline), furazolidone (the drug that has been most commonly used to treat childhood cholera), and trimethoprim-sulfamethoxazole have been reported from Asia (including Bangladesh), Africa and Latin America [10-17]. Currently, over 90% of the *V. cholerae* O1 isolates at the treatment centres of ICDDR,B are resistant to trimethoprim-sulfamethoxazole and furazolidone, and approximately 30% are resistant to tetracycline.

Because of the high prevalence of multiply-resistant strains of *V. cholerae* and the lack of alternative agents, erythromycin has become the first-line therapy for cholera in children at the ICDDR,B. Erythromycin is administered in multiple doses for 3 days, and it has a high incidence of gastrointestinal adverse events. Because of the problem of resistance, and the lack of a drug safe for use in children that has been demonstrated to be effective when given as single-dose, we propose to study the efficacy of single-dose azithromycin therapy in childhood cholera. Based on a number of attributes of azithromycin, as summarized in the following section, it is reasonable to think that this drug, known to be safe for use in children, would be effective as single dose therapy for cholera in children.

Activity, Pharmacokinetics, and Safety Profile of Azithromycin

The good *in vitro* and *in vivo* activity of erythromycin against intracellular pathogens has been a stimulus for development of the new generation of macrolides. Four new generation macrolides including azithromycin have been synthetically derived from erythromycin through modification of its chemical structure [18,19]. These alterations resulted in better resistance to

the range of pH found in the stomach, and thus better oral bioavailability. They also have better *in-vitro* activity against many pathogens, achieve higher intracellular concentrations, have longer half-lives allowing infrequent dosing, and better tolerability than erythromycin [19-22].

Azithromycin inhibits bacterial protein synthesis by binding to the 50S component of 70S ribosomal subunit. It is 300 times more stable in the range of stomach pH than erythromycin, and has higher oral bioavailability (37% versus 25%). Its absorption, however, is reduced by about 50% in presence of food and antacids [23-25]. After a 500 mg oral dose, a peak serum concentration of 0.4 mg/l is reached in 2-3 hours, and its trough serum concentration 24 hours after a dose is 0.04 mg/l [24,26]. The agent has a low affinity for serum proteins, and protein affinity decreases with increasing serum concentrations of the drug (protein binding of 50% and 12% at drug concentrations of 0.05 mg/l and 0.5 mg/l respectively) [26]. Once the serum peak is reached, concentrations then sharply decline, indicating a rapid distribution phase and a high (23 l/kg) volume of distribution [23,24,26].

Azithromycin is eliminated without significant metabolism; <5% of the drug is demethylated in the liver to inactive metabolites [24]. Its primary route of excretion is biliary and transintestinal. This ensures high stool concentrations of the drug [24]. In our recently completed study of azithromycin in adults with shigellosis, the median stool concentrations on study days 2 and 4 (after 500 mg on admission followed by 250 mg at 24-hour intervals) were 196 micro gram/gram of stool and 387 micro gram /gram of stool [38]. With the exception of antacids, no major interactions have been noted between azithromycin and commonly used drugs [25]. Dose adjustment is only required for patients with severe renal insufficiency (creatinine clearance <40 ml/min.) or hepatic failure [25]. The pharmacokinetic properties of azithromycin are similar in adults and children [25,27].

The better *in-vitro* activity of azithromycin compared to erythromycin and other newer macrolides is due in part to its better penetration of the cell wall of gram-negative bacteria [18,28-32]. Several *in vitro* studies have found azithromycin to be active against *H. influenzae* [29] as well as common enteric pathogens including *Escherichia coli*, *Salmonella*, *Campylobacter*, *Shigella* and *Vibrio cholerae* [30]. The MIC of azithromycin against *Enterobacteriaceae* is influenced by the pH of the media. Values are lower in alkaline pH [33,34] - the usual environment for *V. cholerae*. While erythromycin is generally considered as bacteriostatic, azithromycin is considered bactericidal due to its sustained high concentrations in infected tissues [35].

Data on 3,995 patients treated with azithromycin in the United States and Europe in phase II and III trials indicate that its tolerability is comparable to commonly used drugs such as penicillin, amoxicillin and oral cephalosporins, and is markedly better than erythromycin [25,27]. These studies were done on patients with respiratory, sexually transmitted and skin infections, and the total dose used was 1.5 g (500 mg on the first day and 250 mg daily for 4 days). Gastrointestinal disturbances were the most common adverse effects noted; diarrhoea was reported to occur in about 4%, nausea in 3%, and abdominal pain in 3% of the patients. Sixty percent of these adverse events were characterized as mild [25]. This rate of adverse events is much lower than that observed with erythromycin. Severe adverse events were noted in 7% of patients treated with azithromycin compared to 14% of patients treated with other antimicrobial agents, and serious adverse events requiring withdrawal of drug were reported in only 0.7% of the patients taking azithromycin [25]. Interestingly, unlike most antimicrobial agents, adverse events in association with azithromycin were both less common and less serious in children than in adults [25,27]. Azithromycin was not associated with major or consistent effect on laboratory measures of hematological, hepatic or urinary function [25].

Research Design and Methods

Describe in detail the methods and procedures that will be used to accomplish the objectives and specific aims of the project. Discuss the alternative methods that are available and justify the use of the method proposed in the study. Justify the scientific validity of the methodological approach (biomedical, social, or environmental) as an investigation tool to achieve the specific aims. Discuss the limitations and difficulties of the proposed procedures and sufficiently justify the use of them. Discuss the ethical issues related to biomedical and social research for employing special procedures, such as invasive procedures in sick children, use of isotopes or any other hazardous materials, or social questionnaires relating to individual privacy. Point out safety procedures to be observed for protection of individuals during any situations or materials that may be injurious to human health. The methodology section should be sufficiently descriptive to allow the reviewers to make valid and unambiguous assessment of the project. (DO NOT EXCEED TEN PAGES, USE CONTINUATION SHEETS).

1. STUDY DESIGN

Prospective, randomized, double-blind, controlled clinical trial

2. SELECTION OF PATIENTS FOR THE STUDY

A total of 116 evaluable children required to be enrolled for this study will be selected from those who attend the Dhaka Hospital of ICDDR,B according to the following selection criteria:

2.1 Inclusion criteria

- Age / Gender: 1-15 years (male) or 5-15 years (female)
- Duration of illness: 24 hours or less
- Written informed consent for participation in the study from either parent/ guardian
- Severe dehydration according to WHO guidelines [32]
- Positive stool dark-field microscopic examination for *V. cholerae* (pre-enrollment), and isolation of *V. cholerae* O1 or O139 (post-enrollment) from a pre-therapy stool and/or rectal swab culture.

2.2 Exclusion criteria

- History of receiving > 1 dose of an antimicrobial agent effective in the treatment of the isolated strain of *V. cholerae*, or even a single dose of azithromycin.
- Concomitant infection requiring antimicrobial therapy which may interfere evaluation of efficacy and/or safety of the study drugs.
- A concomitant illness that may interfere with the evaluation of outcome.
- Patients with chronic renal, cardiac, or hepatic problems.

Note: Patients will be enrolled at any time of the day, and on any day of the year, subject to fulfillment of enrollment criteria.

3. OBSERVATIONS AND MEASUREMENTS

3.1 Base-line observations and management

Male children, aged 1-15 years, who are brought to the Dhaka Hospital of ICDDR, B for their watery diarrhoea of \leq 24 hours and signs of severe dehydration, and those who have not received any antimicrobial therapy for their diarrhoea will be initially screened for the study. They will be admitted into the Clinical Study Ward of the Dhaka Hospital and weighed (dehydration weight). Their vital signs and dehydration status will be recorded, and then they will be rehydrated using "Rice ORS" (3.5, 2.9, 1.5 and 50 grams of sodium chloride, trisodium citrate, potassium chloride and dried rice powder respectively for preparation of 1.0 litre of solution) or "Dhaka Solution", an intravenous polyelectrolyte solution (133,

Principal Investigator: Last, first, middle: [name]

13, 98 and 48 mmol/l of sodium, potassium, chloride and bicarbonate/1.0 litre of solution respectively) in accordance with the WHO guidelines [32]. This period will be named as "Rehydration Period" and will be about 3-4 hours in duration. During this period, a stool specimen will be sampled for dark field microscopic examination for demonstration of *V. cholerae*. Patients will be reexamined to ensure that all clinical signs of dehydration has disappeared.

3.2 4-hour, "Observation Period"

After "Rehydration Period" is over, children will be observed for another four-hour period, to be called "Observation Period". This is the maintenance phase, and the period will also be used to determine severity of illness; a stool output of \approx 5.0 ml/kg.hour during this period will be considered as indicative of a severe disease. Rice ORS will be the maintenance fluid for all patients, however, patients with severe, persistent vomiting (usually \approx 4/hour) or a very high rate of purging (usually \approx 10 ml/kg.hour) may require intravenous fluid for maintenance of hydration. Patients will be allowed to drink plain water *ad libitum* during this period, and intake and output records will be carefully maintained.

3.3 Final inclusion in the study

Patients who have a stool output of \geq 5.0 ml/kg.hour during the observation period and have evidence for infection with *V. cholerae*, as demonstrated by dark field microscopic examination of their freshly passed stool specimen, will be eligible for final enrolment in the study, and their parents/guardians will be requested for their consent.

3.4 Admission history and physical examination

Upon final inclusion into the study, an elaborate medical history will be obtained and a thorough physical examination, including assessment of dehydration, will be performed. All findings will be recorded in pre-designed data collection forms.

3.5 Treatment regimen and randomization

After informed consent has been obtained, patients will be randomly assigned in equal numbers to receive either a single 20 mg/kg (maximum 1.0 g) dose of azithromycin oral suspension, or 12.5 mg/kg (maximum individual dose of 500 mg) of erythromycin oral suspension every 6 hours for 3 days (12 doses). Upon final enrollment in the study, patients will be assigned consecutive study numbers which will have been randomly pre-assigned to one of the two treatment regimen using a computer generated set of random numbers and a block randomization method using a fixed block length of 4.

The time of administration of drug will be considered as the beginning of the study, and each consecutive 24-hour period from this time will constitute a study day. For patients who vomit within 10 minutes of ingestion of the study drug, the dose will be repeated and the event will be recorded; incidence of repeat dosing will be compared between the two study groups at the time of analysis.

A double dummy technique will be used in order to blind treatment regimen; study drugs will be made available in two colour coded bottles "A" and "B" for each study children. For children in the azithromycin treatment group, bottle "A" will contain active drug and bottle "B" will contain a placebo for erythromycin. For children in the erythromycin treatment group, bottle "A" will contain placebo for azithromycin and bottle "B" will contain active erythromycin. For all study patients, the first dose of study medication will be dispensed from both of the bottles "A" and "B" and the remainder of the doses will be dispensed from bottle "B". Active and placebo for azithromycin and erythromycin will be identical in

appearance, and their concentration will be adjusted to allow dispensing drug as ml/kg of body weight basis (identical in volume/kg). Random numbers will be generated by Pfizer, USA, who will also provide coded drugs for this study.

In the event of occurrence of vomiting within 10 minutes of administration of the study drug, the dose will be repeated. In the event this leads to short-fall in the amount of drug required, which will be a rare event, extra sets of both study drugs (same colour coding) will be made available. These extra bottles will be retained by the same person withholding randomization code, to be broken in the event of emergency, however, s/he will not be involved with the study in any way; on assessing the need s/he will dispense the right set of bottles in response to the investigators requests.

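### The protocol tells the enrolling investigators that blocks have a fixed length of 4; varied, undisclosed lengths would be a cheap, minor improvement

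*Protocol*

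**What the plan says.** All of the allocation rules stand in Protocol section 3.5.

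- Ratio: "patients will be randomly assigned in equal numbers to receive either" one of the two regimens.
- Sequence: "patients will be assigned consecutive study numbers which will have been randomly pre-assigned to one of the two treatment regimen". No stratification is stated.
- Blocks: "a block randomization method using a fixed block length of 4".
- Blinding: "A double dummy technique will be used in order to blind treatment regimen". Every child takes the first dose from bottles A and B and all later doses from B.
- Matching: the sentence beginning "Active and placebo for azithromycin and erythromycin will be identical in" goes on to name appearance, and concentrations are adjusted so as to allow "dispensing drug as ml/kg of body weight basis (identical in volume/kg". Taste and smell are not mentioned.
- Custody: the drug manufacturer generates the random numbers and is the party "who will also provide coded drugs for this study". The emergency code stays with a person outside the study.

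Elsewhere, the background says of erythromycin that "it has a high incidence of gastrointestinal adverse events", and the summary expects fewer adverse events with azithromycin. The informed consent section makes the investigator responsible for obtaining consent, and the budget justification has the investigators giving the clinical care.

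**The concern.** A short block of known, constant length lets anyone who can infer earlier arms work out something about the next one. The people best placed to do this are the investigators. They see how earlier children respond, they have the block length in their own protocol, and they use study numbers in strict order.

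A possible source of inference is the expected difference in gastrointestinal tolerability between the arms. Another is any perceptible difference between active and placebo suspensions beyond appearance and volume.

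The stake is selection at entry. Section 2.2 contains exclusions that need judgement, for a concomitant illness or infection that may interfere with evaluation. Under section 3.3, consent is sought only after severity and dark-field results are known. An investigator who expected a particular arm next could apply that discretion unevenly, even without intending to.

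**Working it through.** **The plan's own figures.** The protocol gives no figure for predictability. Its sample size (section 3.6) does not depend on block length: 2 × 0.95 × 0.05 × (1.645 + 0.842)² / 0.10² = 58.7 per arm, against the stated 58. The planned enrolment of about 160 corresponds to 160 / 4 = 40 blocks.

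**Step 1: all earlier arms known, fixed block of 4.** There are six equally likely orders: AABB, ABAB, ABBA, BAAB, BABA, BBAA.

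| Position in block | Chance that the arm is certain | Best guess is right |
|---|---|---|
| 1 | 0 | 1/2 |
| 2 | 0 | 2/3 |
| 3 | 1/3 (first two match) | 1/3 × 1 + 2/3 × 1/2 = 2/3 |
| 4 | 1 | 1 |

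- Certain: (0 + 0 + 1/3 + 1) / 4 = 33.3%.
- Guessed correctly: (1/2 + 2/3 + 2/3 + 1) / 4 = 70.8%.

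One known arm at the start of a block therefore gives 2/3 for the next child. Two known arms settle the third only if they match. Otherwise the third is an even chance.

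**Step 2: earlier arms guessed with error.** An optimal guesser was simulated over runs of 160 allocations. The guesser knows either the fixed length or only the set of possible lengths, and judges each earlier child's arm correctly with probability q. The values of q are assumptions, since the protocol offers none. The table gives the percentage of next allocations guessed correctly.

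| q | Fixed 4 | Random 4/6/8 | Random 2/4/6 |
|---|---|---|---|
| 50% (blind intact) | 50 | 50 | 50 |
| 70% | 56 | 54 | 55 |
| 80% | 60 | 57 | 58 |
| 90% | 65 | 60 | 62 |
| 100% | 71 | 68 | 70 |

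**Step 3: near-certain allocations**, meaning those predictable with more than 90% confidence.

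- At q = 100%: about 33% for fixed 4, 5% for 4/6/8 and 6% for 2/4/6.
- At q = 90%: about 1% for fixed 4 and none for either varied scheme.
- At q of 80% or less: none under any scheme.

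**Step 4: choice of lengths.** A block of 2 makes its second allocation certain once the first is known, so it is guessable (1/2 + 1) / 2 = 75% of the time, more than a block of 4. This is why a set that includes 2 gains so little over fixed 4.

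**The case against.** The case for leaving the plan alone is substantial.

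- **The safeguards come first.** Double dummy, equal volume per kg, manufacturer-coded drug and an outside code holder must all in effect be bypassed before block length matters. With guesses at chance, every scheme gives 50%. This stands.
- **The routes to unblinding are uncertain.** A reader might infer from the silence on taste and smell that the suspensions differ. The protocol does not say so, and a child who receives one version of bottle B twelve times has nothing to compare it with. Vomiting and diarrhoea belong to cholera itself, and the background reports gastrointestinal disturbance as azithromycin's commonest adverse effect too. This stands: guess accuracy is unknown and may be close to chance.
- **Entry and primary outcomes are largely measured.** Stool output, dark-field microscopy and culture govern entry. Watery stool has a physical definition, and bacteriological success rests on culture. Attendants do the initial screening. This limits selective enrolment but does not remove it, because consent and the section 2.2 exclusions leave discretion with the investigators. A guessed arm could also colour later judgements, but block length does not change that.
- **The gain is modest.** At 70 to 80% accuracy, lengths of 4, 6 and 8 lower correct guesses by only two to three percentage points. This also stands. The clear gain is in near-certain allocations, and only if earlier arms are effectively known.

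A reader might also infer that any guessed arm makes the next allocation predictable. Step 1 shows otherwise: one arm gives 2/3, and certainty needs two matching arms or three known arms in the same block.

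**Conclusion.** The point holds as a minor weakness. The protocol fixes a short block length and discloses it to the people who enrol, leaving the blind as the only barrier between the printed scheme and prediction. The exposure runs from nothing (blind intact) to one third of allocations certain and 71% guessable (all earlier arms known). The middle of the range, 56 to 60% against 50%, rests on an assumed 70 to 80% accuracy that no statement in the protocol supports or excludes. All figures assume an optimal guesser who has formed a view of each earlier child before the next is enrolled, so they are upper values for that accuracy.

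The protocol does not support concluding that the blind will fail or that the comparison will be biased, and the size of any bias cannot be derived from it. The sample size is unaffected.

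**What to change.** Before the list is generated, replace the fixed length in section 3.5 with block lengths drawn at random from 4, 6 and 8. Remove the lengths from the protocol, saying only that permuted blocks of varying size are used, and let the list generator alone hold them. Do not include length 2.

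Section 3.5 speaks of the random numbers as still to be generated, so on the text the list costs nothing to change. The one statistical cost is balance: stopping part-way through a block of 8 can leave the arms four children apart, against two with blocks of 4. That is small beside about 160 enrolled.

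As a secondary clarification, state whether active and placebo suspensions also match in taste and smell. If they do not yet match, the supplier would have to match the flavour.
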